#### All standard study meetings, meeting content, and duration are summarized here:

\* Indicates MRI procedures to be completed only by participants who are eligible for MRI scanning (n=60).

a Times listed in the table are approximate.

bMRI Scan 4 only for participants showing biologically verified abstinence at 3-month follow-up.

Intentions and expectations for the psilocybin session will be discussed. Furthermore, a structured cognitive-behavioral smoking cessation intervention will be implemented throughout the course of these meetings to prepare participants for smoking abstinence and potential withdrawal. Throughout the preparatory meetings, participants will be encouraged to view the psilocybin session as providing an opportunity for deep reflection about the role of smoking in their lives. The purpose of the psilocybin session is to enhance motivation for initiating a quit attempt. Procedures for drug administration and the conduct of the session will be similar to

procedures used in our previous (Griffiths et al., 2006, 2008, 2011) and ongoing studies with psilocybin (IRB # NA\_00001390 in cancer patients; IRB # NA\_00020767 in healthy adults), and are described below in the section "Conduct of Psilocybin Sessions."

Participants will meet with study staff for debriefing one or two days after the psilocybin session. Participants will then meet weekly with study staff for 2 weeks after their psilocybin session (i.e., in weeks 6 and 7), and at 2-week intervals until the end of the 13-week study treatment (i.e., in weeks 9, 11, and 13). The general purpose of the meetings following the session is to provide a context for discussing and integrating experiences from the psilocybin session, and to provide support for smoking cessation. Additional contact hours will be scheduled if it is judged that the participant would benefit from further meetings with study staff to discuss experiences from the session or provide additional support for smoking abstinence. Aside from the psilocybin session and MRI scan visits (if applicable), all meetings may be held remotely using a secure online platform, including use of remote CO monitoring and mailed in or at home urine sample testing.

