Conduct of Psilocybin Session: Participants in the psilocybin condition, as well as those in the NRT condition who elect to undergo an optional psilocybin session after the 6-month follow-up, will be instructed to consume a low-fat breakfast before reporting to the laboratory for the psilocybin session. Participants must refrain from smoking during the time of drug action on the

psilocybin session day. On the day of the psilocybin session, the last cigarette may be smoked 1 hour before psilocybin administration. Participants will be instructed to abstain from smoking and drinking alcohol for at least the next 24 hours until the post-psilocybin MRI scan has been conducted (when applicable).

Before drug administration, participants will provide a urine sample for a drug urine screen and, for females, for pregnancy testing. Sessions will not proceed unless drug tests are negative for illicit drug use, and pregnancy tests are negative. Psilocybin capsules will be administered with approximately 100 mL water. The study staff, under the supervision of the investigators, will be present in the room and available to respond to participants' physical and emotional needs during the full course of the session (at least 7 hours).

These sessions often require session facilitator(s) and the participant to be in a session room together for an extended period of time and may require periods of physical contact (e.g. for adjusting blood pressure cuff, therapeutic touch etc.). On session days, it is possible that participants may inadvertently remove PPE while under the influence of psilocybin. We will adhere to the following additional safety measures for these sessions:

- COVID-19 testing will be available for participants and facilitators prior to these meetings if there is special concern raised about the possibility of exposure during the final preparation or drug administration day. The availability of testing will be discussed during preparation.

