NRT Condition: Participants in the NRT condition will receive preparation and instructions from study staff on how to use the nicotine transdermal patch, which may be mailed to them to reduce in-person contact. Participants will receive detailed information on NRT and potential side effects prior to patch administration. On the day after their Target-Quit Date in week 5, they will be provided with a 2-week supply of medication, and instructed to begin a standard 8 to 10 week transdermal nicotine patch regimen according to recommended label usage (For individuals who smoke more than 10 cigarettes per day: 21mg daily for weeks 1-6, 14mg daily for weeks 7-8, 7mg daily for weeks 9-10. For individuals who smoke 10 or less cigarettes per day: 14mg daily for weeks 1-6, 7mg daily for weeks 7-8; FDA label, PDR.net). For MRI participating volunteers receiving NRT (n=25), the Target-Quit Date will occur 24 hours prior to the MRI scanning day in week 5, and participants will begin using NRT immediately after that MRI scan is completed. To ensure matching treatment procedures, participants randomized to the NRT condition who are not MRI participating volunteers, and are completing only the treatment portion of the protocol (n=15), will also stop smoking 24 hours prior to their meeting in week 5 (to be confirmed by breath CO). At this meeting they will receive their first 2-week supply of transdermal nicotine patches and initiate NRT use. Participants will receive additional supplies of appropriate dose patches at 2-week intervals around their regularly scheduled treatment meetings. Participants will be asked to notify study staff immediately in case of adverse events or side effects, and will determine with the study physician whether NRT dosage should be adjusted, or permanently discontinued. In the unlikely event of a severe side effect such as a myocardial infarction/arrhythmia, participants will be advised to immediately discontinue NRT use. Under these circumstances, participants will be asked to continue the study protocol meetings to completion.

After completing the 6-month follow-up, participants initially randomized to the NRT condition will be eligible to undergo an optional high-dose (30mg/70kg) psilocybin session. If they choose to take part, they will receive two weekly preparation meetings, one high-dose

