#### Inclusion criteria for MRI scanning eligibility only:

- 21 to 65 years old
- Agree to abstain from smoking and alcohol for 24-hours, and caffeine for 12-hours prior to MRI scanning\*
- Be right-handed\*

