#### Measure taken the day after psilocybin session (psilocybin condition only):

*Next-day Monitor Rating Form*: On this form, which was used in our previous study of psilocybin (Griffiths et al., 2006), study staff will rate the qualitative nature of the session the day after each session after meeting with the volunteer.

*Headache Interview Form:* This 14-item interview assesses incidence, duration, and severity of headache during or immediately after psilocybin sessions, as headaches have been found to occur in some individuals post-psilocybin (Johnson et al., 2012).

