Continuation of Data Collection: To the extent possible without interfering with appropriate medical response to any adverse effects, we will continue collecting data from volunteers even if adverse effects occur that warrant stopping study participation. Thus, "stopping study participation," means stopping or delaying any study procedures that would interfere with appropriate medical response and care. The study data collection procedures entail minimal risk - interviews and questions and ratings. They represent the scientific and societal benefit aspects of this study and we believe they should be continued to the extent possible.

**Exiting the Drug Session:** Participants will remain under observation at least 7 hours and until subjective and objective drug effects have subsided. Participants will be released into the custody of a close friend or family member who has agreed to take charge of the study participant as a condition of leaving the testing facility. In the unlikely circumstance that the friend or family member is unable to pick up the volunteer from the laboratory as scheduled, a staff member will escort the participant home by taxi. Both the study staff and medical personnel will be on call for 24 hours following the drug session in order to assist with any post-session adverse reactions. Although we expect that all drug effects will have subsided and that participants will be ready to leave BPRU 7 to 10 hours after drug administration, participants will be kept overnight and under observation the next day if we judge it to be indicated.

**Post-session Headache:** Because preliminary observations suggest there may be an association between psilocybin administration and transient headache starting about 7 hours after administration, on the first meeting after each session, study staff will conduct a formal interview with the volunteer about post-session headache onset, duration and severity.

**Persisting visual perceptual effects:** To assess for possible persisting visual perceptual effects after psilocybin administration, a questionnaire is included to document the occurrence of various visual phenomena such as changes in color intensity, after-images, and apparent movement of stationary objects. This questionnaire is completed at screening, approximately 1 week after the psilocybin session and at approximately 3, 6, and 12 months after the psilocybin session.

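### The structured headache interview is given only after psilocybin, so its rate cannot be separated from background headache on the quit day, though NRT participants could be asked the same questions at an existing visit

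*Combined protocol and SAP*

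**What the plan says.** **The interview.** Section 7b (Post-session Headache) refers to a possible association between psilocybin and "transient headache starting about 7 hours after administration", and for that reason "on the first meeting after each session, study staff will conduct a formal interview with the volunteer about post-session headache onset, duration and severity". Section 6b puts the form under the heading "Measure taken the day after psilocybin session (psilocybin condition only" and describes it thus: "This 14-item interview assesses incidence, duration, and severity of headache during or immediately after psilocybin sessions".

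**Timing in the psilocybin arm.** Section 3a says: "Participants will meet with study staff for debriefing one or two days after the psilocybin session". On the session day, "the last cigarette may be smoked 1 hour before psilocybin administration". Smoking is then ruled out for at least 24 hours (section 3a) or at least 30 hours after the capsule (section 4). The MRI criteria in section 4 add: "Agree to abstain from smoking and alcohol for 24-hours, and caffeine for 12-hours prior to MRI scanning". The post-session scan is one day after dosing.

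**The NRT arm.** Under section 3a (NRT Condition), scanned participants stop smoking 24 hours before the week-5 scan and start the patch after it. Unscanned participants "will also stop smoking 24 hours prior to their meeting in week 5 (to be confirmed by breath CO", and receive their first patches at that meeting.

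**What both arms receive.** There is an open enquiry about well-being at each treatment meeting after the quit date (Adverse Events Form, 6b). Brief calls or texts are made on most of the first seven days (Monitor Telephone Contact, 3a). A COVID-19 symptom questionnaire for in-person visits includes headache among its items (3a). Section 6c contains no headache analysis, and no section gives a rule for attributing a headache to a cause.

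**The concern.** The interview exists to examine a suspected drug effect, but it is given only to people who have taken the drug and who are also in their first day of a quit attempt. Whatever headache would have occurred in those hours without psilocybin is included in the rate, and nothing in the plan allows it to be taken out.

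The control arm could supply that background rate. Its participants go through a similar abstinent day before any patch, and they attend a scheduled meeting at its end. They are not asked the same questions. If headaches were later tabulated by arm, one arm would have been asked systematically about onset, duration and severity, while the other would have been reached only by less specific routes. Such a table could show an excess under psilocybin from the difference in questioning alone.

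The secondary objective is to gather clinical experience that helps design later controlled trials. A headache rate that cannot be interpreted is of limited use for that.

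**Working it through.** The documents state no headache rate or headache calculation, so there is no figure to reproduce. The timing can be checked from the protocol's own hours. The rest is illustration with assumed rates.

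**1. Overlap with tobacco abstinence.** The last cigarette may be 1 h before the capsule and expected onset is about 7 h after it, so the participant may be as little as 1 + 7 = 8 h tobacco-free at onset. The period from 7 h to 24 h after the capsule lies wholly inside the required abstinence, whether that is read as 24 h or 30 h.

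**2. Overlap with the caffeine rule.** This applies only to scanned participants: 25 of 40 (63%) or 30 of 50 (60%), depending on which of the protocol's sample sizes applies. Usual caffeine is taken on the session morning (section 4). For a scan starting S hours after the capsule, the restriction starts at S − 12, and its share of the time from expected onset to scan is 12/(S − 7). The protocol says only one day, so S is an assumption:
- S = 20: starts at 8 h; share 12/13 = 92%
- S = 24: starts at 12 h; share 12/17 = 71%
- S = 30: starts at 18 h; share 12/23 = 52%

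In each case the restriction begins after the expected 7 h onset, so the overlap is partial.

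**3. What one arm cannot show.** Let b be the background rate and d the psilocybin-caused rate, both assumed and taken as independent. The observed rate is p = b + d − bd, and the share of those reporting headache who would have had one anyway is b/p.
- d = 20%, b = 5%: p = 24%, share 0.05/0.24 = 21%
- d = 20%, b = 30%: p = 44%, share 0.30/0.44 = 68%
- d = 40%, b = 5%: p = 43%, share 0.05/0.43 = 12%
- d = 40%, b = 30%: p = 58%, share 0.30/0.58 = 52%

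Data from the psilocybin arm alone cannot tell these cases apart.

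**4. Unequal ascertainment.** Suppose no drug effect, full capture by the interview, and a fraction c captured by the NRT arm's routes. The apparent risk ratio is 1/c: 1/0.8 = 1.25 and 1/0.3 = 3.3. At b = 20%, c = 50% and 50 per arm, that is 50 × 0.20 = 10 participants against 10 × 0.5 = 5. This only restates the assumed c; it shows the direction and does not estimate the bias.

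**5. Precision if both arms are asked.** The 95% half-width of the difference is 1.96 × √{[p(1 − p) + b(1 − b)]/n}. Over b = 5–30% and d = 20–40%:
- n = 50: from 1.96 × √[(0.1824 + 0.0475)/50] = 13 points to 1.96 × √[(0.2464 + 0.21)/50] = 19 points
- n = 40: 15 to 21 points by the same formula

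For the split by MRI participation, with 25 scanned and 15 unscanned per arm, b = 20% and d = 20% (p = 36%): 1.96 × √(0.3904/25) = 24 points and 1.96 × √(0.3904/15) = 32 points.

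**The case against.** Much of the opposing case is sound.

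- **Cause.** A reader might infer that quitting, caffeine restriction or scanning produces headache here. The documents do not say so. The withdrawal symptoms in section 7a do not include headache, and the withdrawal scale in 6b has no headache subscale. The point does not need that premise: any background headache, whatever its cause, is mixed into a one-arm rate.
- **Attribution.** A reader might also infer that such headaches will be counted as psilocybin effects. No attribution rule and no table of adverse events by arm is planned, so the supportable statement is that they cannot be separated.
- **Other enquiry.** It would be wrong to say that NRT headaches can surface only through the open adverse-event question. The COVID-19 screen and the daily contacts could also pick them up. Neither is described as recording onset, duration and severity, and the screen is tied to in-person visits.
- **Internal contrasts.** Unscanned psilocybin participants have no scan or scan-related caffeine rule, and recorded onset time helps to distinguish a 7-hour headache from a later one. Both help with the scan restrictions. Neither removes the first day off tobacco, which all share. Optional sessions in NRT participants already abstinent would be informative, but it is unclear whether the interview applies to them.
- **An imperfect control.** NRT participants have no equivalent of a long session under eyeshades with music, or of nitroglycerin, for which headache is a listed reaction. Recall is one or two days against about 24 hours, and treatment is open. These limits stand. Asking both arms the same questions is still more informative than a one-arm rate.
- **Purpose.** The interview is risk monitoring, where asking more errs towards caution. That supports a minor rating.

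**Conclusion.** The concern holds in a limited form. The structured interview has no NRT counterpart at the quit attempt. Its window falls within the first day off tobacco for everyone in the psilocybin arm, and partly within the caffeine restriction for the scanned 60–63%. The psilocybin headache rate therefore cannot be separated from background headache, and a comparison by arm, if made, would rest on unequal ascertainment. The direction of that inequality is clear; its size is unknown, since every rate used above is an assumption.

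Severity is minor. This is a weakness in safety measurement and does not affect the primary abstinence outcome. Two inconsistencies bear on it. Section 6b restricts the form to the psilocybin condition, while 7b refers to each session, which could include the optional sessions of NRT participants. The NRT quit date is 24 hours before the week-5 visit in the NRT Condition text, but the timeline table shows it at the week-5 scan and again at meeting 6 in week 6.

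**What to change.** - Ask NRT participants the same headache questions at treatment meeting 5, before the first patch. In both arms, anchor the comparison to the first 24 hours after the last cigarette, and record the time of interview.
- In 6b, list the form for both arms. State whether it is also given after the optional sessions of NRT participants, so that 6b and 7b agree.
- Reconcile the NRT quit-date timing between the timeline table and the NRT Condition text, so that the window is the same for everyone.
- In 6c, report headache incidence by arm, with the risk difference and its 95% confidence interval, also split by MRI participation. Call it descriptive, and state that session conditions and recall interval are not matched.

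The cost is one short interview for 40 to 50 NRT participants at a meeting that already takes place, plus rewording of the form's time anchor. No visit or procedure is added and treatment is unchanged.

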#### c. Plan for reporting unanticipated problems or study deviations.

The investigators will report adverse events to the IRB according to the Johns Hopkins and federal guidelines.

#### d. Legal risks such as the risks that would be associated with breach of confidentiality.

While breach of confidentiality could be embarrassing and disturbing, study records involve no documentation of specific illegal acts.

#### e. Financial risks to the participants.

There will be no financial risks to participants.

#### 8. Benefits

#### a. Description of the probable benefits for the participant and for society.

The probable benefits from the study for participants is a possible cessation or reduction in cigarette smoking and nicotine dependence. Furthermore, for participants in the psilocybin condition, some mental health and religious professionals have reported that hallucinogens, under specific circumstances of administration, can provide unusual opportunities for deep reflection. However, no such benefit from the drug session can be promised to volunteers in this study. All volunteers may benefit from the general review of life values and direction that will occur in meetings with the study staff over a period of several months. Society will benefit from gaining a more detailed understanding of the effects of psilocybin on smoking cessation or for other forms of substance dependence. Additionally, the proposed neuroimaging portion of the study will produce novel findings with regards to the intermediate (i.e., next-day) effects of psilocybin, and how these may contribute to longer-lasting behavioral and psychological changes, including smoking cessation.

#### 9. Payment and Remuneration

### a. Detail compensation for participants including possible total compensation, proposed bonus, and any proposed reductions or penalties for not completing the protocol.

Volunteers will not receive monetary compensation for the treatment portion of the study (i.e, treatment meetings, follow-ups). However, MRI participating volunteers (n=60) will receive an hourly compensation of \$20/hr. for all MRI scanning days, including participation in the preliminary NIDA sub-study protocol (possible total compensation=\$480). Funding for this compensation will be provided by NIDA IRP. In order to match potential earnings between all MRI participating volunteers, those who do not undergo a paid 3-month follow-up MRI scan (i.e., who are smoking at that time) will be compensated at a \$20/hr. rate for their time during the 3-month follow-up. Funding for this compensation will be provided by the research study budget. No penalties will be assessed for not completing the protocol. Volunteers will receive free parking vouchers for all scheduled study visits.

#### 10. Costs

### a. Detail costs of study procedure(s) or drug (s) or substance(s) to participants and identify who will pay for them.

Other than travel to and from the study site, there are no costs to participants. All treatment counseling and pharmacotherapy will be provided at no cost to the participant. Furthermore, participants and family or friends who pick up participants after psilocybin sessions will be provided with free parking vouchers for all in-person meetings.

